### **11.5.3. Time to Return to Usual Health**

Definitions:

Return to Usual Health

“Yes” response to the daily FLU-PRO global assessment question, “Have you returned to your usual health today?” maintained for at least two

	consecutive daily diary periods without symptom relief medication during or between those two daily diary periods
Time of Return to Usual Health	The time of the first diary entry in which the subject achieves Return to Usual Health
Time to Return to Usual Health	Time (hours) from first dose to the Time of Return to Usual Health

#### Variables Used for the Analysis

The analysis will require the following variables:

**Table 11: Variables Used for Analysis of Time to Return to Usual Health**

Variable	Source	Format/Notes
Date and time of first medication intake	CRF	
Date and time of completion for each symptom assessment record	Subject diary	
Return to usual health global assessment question response	Subject diary	The return to usual health question will have possible response values of “Yes” or “No”. In the event that the response was not recorded at a specified time point (e.g., Day 2), the missing data will not be imputed.
Date and time of symptom relief medication intake	Sponsor-provided listing	The list of symptom relief medications will be selected from the listing of all concomitant medications prior to unblinding.

#### Analysis

The efficacy parameter, Time to Return to Usual Health, will be derived as follows:

Event: Time of Return to Usual Health – time of the first dose

Censored: Time of last diary assessment – time of the first dose

If Return to Usual Health is achieved at the time of the first symptom assessment diary record, the subject will be excluded from the analysis.

If the subject does not achieve Return to Usual Health prior to the subject’s last available diary assessment, but records a “Yes” for the return to usual health global assessment question at the last available diary assessment with no evidence of symptom relief medication intake during that diary period, time of Return to Usual Health will be considered to have occurred at the time of the last available diary assessment.

Time to Return to Usual Health for the NTZ treatment group will be compared to that of the placebo treatment group using a Gehan-Wilcoxon test stratified by (1) time from

onset of illness to time of first dose of study medication (0-24, >24-≤36, or >36 hours from onset), (2) pre-enrollment use of symptom relief medication, and (3) presence of underlying lung condition including asthma, COPD, or past or present history of smoking. The comparison will be graphically depicted using Kaplan-Meier curves.

Analysis Population(s): ITTI

Derived Variables: Event: Time of Return to Usual Health – time of first dose

Censored: Time of last usual health global assessment – time of first dose

#### 11.5.4. Change in Virus Titer from Baseline to Day 2, 3, and 7

Variables Used for the Analysis

The analysis will require the following variables:

**Table 12: Variables Used for Analysis of Change in Virus Titer**

Variable	Source	Format/Notes
Quantitative PCR virus titer	Laboratory Data	Quantitative PCR values should be log-transformed for analysis purposes.

Analysis

Mean changes in viral titers from Baseline to Day 2, from Baseline to Day 3, and from Baseline to Day 7 for the NTZ and the placebo treatment groups will be compared using a t-test.

Subjects with undetectable virus by quantitative PCR at Baseline will be excluded from this analysis. Any undetectable result on Day 2, Day 3 or Day 7 will be imputed with the lower limit of detection for the quantitative PCR assay. Any positive result that is below the limit of quantitation will be imputed with the limit of quantitation for the quantitative PCR assay.

Analysis Population(s): ITTI

Derived Variables: Event: Time of Return to Usual Health – time of first dose

#### 11.5.5. Proportions of Subjects with Detectable Virus at Day 2, Day 3, or Day 7

Variables Used for the Analysis

The analysis will require the following variables:

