5.12. Plan for Virology Testing and Monitoring Resistance

Virology testing of nasopharyngeal swab samples will be conducted as described on the following pages.

Table 10: Virology testing of nasopharyngeal swabs

	Day 1	Day 2	Day 3	Day 7	Day 22
RT-PCR by ePlex RPP for Virus Detection	X	X ¹	X ²	X ³	X ⁴
Sequencing for EV/RV Typing	X ⁵				
Quantitative PCR	X ⁶	X ⁶	X ⁶	X ⁷	
Culture & Susceptibility Testing for Resistance Monitoring	X ⁸			X ⁸	X ⁸
Nucleotide Sequencing	X ⁹			X ⁹	X ⁹

¹ If Day 1 sample is negative for EV/RV by RT-PCR² If Day 2 sample is negative for EV/RV by RT-PCR³ Only if one of Day 1, 2, or 3 samples is positive for EV/RV for RT-PCR⁴ If Day 7 sample is positive for EV/RV by RT-PCR⁵ Only the earliest sample positive for EV/RV by RT-PCR of those collected at Days 1, 2, and 3 will be sequenced for EV/RV type⁶ A sample will only be subjected to quantitative PCR if one of the Day 1, 2, or 3 samples is positive for EV/RV by RT-PCR⁷ The Day 7 sample will be subjected to quantitative PCR only if one of the Day 1, 2, or 3 samples AND the Day 7 sample is positive for EV/RV by RT-PCR⁸ If the Day 1 and Day 7 or Day 1, 7, and 22 samples are positive for EV/RV by RT-PCR each sample will be cultured and tested for susceptibility to tizoxanide. Results observed for the Day 7 and Day 22 samples will be compared to the results observed for the Day 1 sample.⁹ Sample pairs exhibiting resistance to tizoxanide will be subjected to sequencing.

1. Collection of samples:

Two nasopharyngeal swabs will be collected from each subject at Baseline (Day 1) and Days 2, 3, 7 and 22.

2. Testing of biological samples:

a. Each Baseline sample will be subjected to RT-PCR using the ePlex® Respiratory Pathogen Panel (GenMark, Carlsbad, CA) to detect influenza A (non-specific as to subtype); influenza A H1, H1N1 (2009), H3 subtypes; influenza B; respiratory syncytial virus A and B (RSV); parainfluenza 1, 2, 3 and 4; human metapneumovirus (hMPV); adenovirus; human EV/RV; coronavirus NL63, HKU1, 229E and OC43; human bocavirus; *Chlamydophila pneumoniae*; *Legionella pneumophila*; and *Mycoplasma pneumoniae*.

b. If a subject's Baseline sample is negative for EV/RV by RT-PCR, his/her Day 2 and Day 3 samples will be subjected to RT-PCR using the ePlex® Respiratory Pathogen Panel to detect respiratory pathogens.

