c. If the Baseline sample or the Day 2 or Day 3 sample is positive for EV/RV, the earliest positive sample will be sequenced to determine virus type and each of the Baseline, Day 2 and Day 3 samples will be subjected to quantitative PCR testing to quantify viral shedding.

d. All Day 7 samples will be subjected to RT-PCR using the ePlex® Respiratory Pathogen Panel. Day 7 samples positive for EV/RV will also be subjected to

quantitative PCR testing to quantify viral shedding if one of the Day 1, 2, or 3 samples was also positive for EV/RV.

- e. Day 22 samples will be subjected to RT-PCR using the ePlex® Respiratory Pathogen Panel only if the sample collected at the preceding time point (Day 7) had detectable EV/RV.
3. Drug susceptibility testing:
 - a. If any Day 7 or Day 22 sample is positive for EV/RV by RT-PCR and one of the Day 1, 2, or 3 samples was also positive for EV/RV, the virus will be isolated (if possible) and tested for susceptibility to tizoxanide (TCID₅₀).
 - b. The Baseline isolate for subjects with virus cultured at Day 7 or 22 will also be tested for susceptibility to tizoxanide, and the results will be compared to the results observed for the Day 7 or 22 isolate.
4. Nucleotide sequencing:
 - a. All Day 7 or 22 samples with resistance ($IC_{50} \geq 10x IC_{50}$ at Baseline) to tizoxanide will be subjected to sequencing. The corresponding Baseline sample will also be subjected to nucleotide sequencing. Initial genotypic assessments of resistance to tizoxanide will focus on isolates displaying the largest shifts in susceptibility.
 - b. Sequencing data for Day 7 or 22 isolates with resistance to tizoxanide will be compared to sequence data for the Baseline sample to identify mutations that may confer resistance.
5. Storage of samples: All samples collected during the study will be stored for at least 2 years for potential future testing.
6. Clinical Virology Laboratory for diagnostic testing:
[REDACTED]

7. Clinical virology laboratory for sequencing, quantification of viral shedding, and susceptibility testing:
[REDACTED]

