- Time to Return to Usual Health for the NTZ and placebo treatment groups will be compared using the Gehan-Wilcoxon test.
- Changes in viral titers from baseline to Day 2, from baseline to Day 3, and from baseline to Day 7 for the NTZ and placebo treatment groups will be compared using a t-test.
- For subjects with laboratory-confirmed EV/RV, the proportions of subjects with EV/RV detected by culture in nasopharyngeal swabs collected at each of Days 2, 3 and 7 will be compared for the two treatment groups using a Fisher's exact test.
- For the ITT population, Time to Symptom Response for the NTZ and placebo treatment groups will be compared using the Gehan-Wilcoxon test.
- For subsets of subjects infected with individual non-EV/RV viruses (e.g., coronavirus), Time to Symptom Response for the NTZ and placebo treatment groups will be compared using the Gehan-Wilcoxon test.

Sensitivity analyses for the primary endpoint will include:

- Repeat the primary efficacy analysis, assigning a Time to Symptom Response of 21 days for subjects that discontinue prior to Day 21 without achieving Symptom Response.
- Repeat the primary efficacy analysis for a "per protocol" subset.
- Repeat the primary efficacy analysis excluding NTZ-treated subjects who reported experiencing chromaturia.

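### Change in viral titer is compared by an unadjusted t-test; ANCOVA on the baseline titer already measured would be at least as precise, at almost no cost (exploratory analysis only)

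*SAP*

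**What the plan says.** SAP 11.5.4 plans three comparisons of change in titer, at Days 2, 3 and 7, each of which "for the NTZ and the placebo treatment groups will be compared using a t-test". Protocol 8.4.1 has the matching sentence: changes "for the NTZ and placebo treatment groups will be compared using a t-test". Neither place names a covariate, the randomization strata or a confidence interval.

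The data rules that matter here are:

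- Scale (SAP Table 12): "Quantitative PCR values should be log-transformed for analysis purposes".
- Baseline restriction (SAP 11.5.4): "Subjects with undetectable virus by quantitative PCR at Baseline will be excluded from this analysis".
- Floor at follow-up (SAP 11.5.4): "Any undetectable result on Day 2, Day 3 or Day 7 will be imputed with the lower limit of detection". Results that are positive but below the limit of quantitation are set to that limit.
- Measurement (Protocol 5.12): once a subject is positive for EV/RV on Day 1, 2 or 3, "each of the Baseline, Day 2 and Day 3 samples will be subjected to quantitative PCR testing to quantify viral shedding".
- Day 7 (Protocol 5.12, Table 10 footnotes): "The Day 7 sample will be subjected to quantitative PCR only if one of the Day 1, 2, or 3 samples" is positive by RT-PCR and the Day 7 sample is positive as well.

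The analysis sits under SAP 11.5, Exploratory Efficacy Analyses. Protocol section 3 also makes every efficacy endpoint outside its three sequential ones exploratory.

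**The concern.** A change score subtracts the whole baseline value. That is the most efficient use of baseline only if follow-up log titer rises one-for-one with baseline log titer. If the slope is below 1, the subtraction adds baseline noise to the outcome. ANCOVA estimates the slope from the data instead.

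A slope of 1 is unlikely under this plan. Setting undetectable follow-up values to the detection limit compresses their spread and flattens the slope. The effect grows with the share of subjects who have cleared the virus, so it should be largest at Day 7.

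What is at stake is the precision of the only between-arm comparison of titer as a quantity; SAP 11.5.5 compares proportions positive. Change in titer is a listed exploratory objective. Day 2 and Day 3 visits are optional, with at least 75% attendance expected, so data are thinner at those days.

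**Working it through.** **Plan's own figure.** There is none to reproduce. Neither document gives an SD, correlation, expected effect or power for titer.

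**Inputs from the documents.** 1:1 allocation; two-sided alpha 0.05 (SAP 11.1); at least 600 EV/RV-positive subjects (SAP 8.3); at least 75% attending Days 2 and 3 (SAP 8.2). If that rate also holds among EV/RV-positive subjects, 0.75 × 600 = 450.

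**Assumed inputs.** Correlation ρ between baseline and follow-up log titer of 0.3 to 0.7; SD ratio k = SD at follow-up / SD at baseline, first 1, then varied; both the same in each arm.

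**Formulas** (large sample, baseline variance set to 1; both share the same sample-size factor):

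- Change-score t-test: variance ∝ 1 + k² − 2ρk
- ANCOVA on baseline: variance ∝ k²(1 − ρ²)
- Share of variance saved = (1 − ρk)² / (1 + k² − 2ρk)

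The slope of follow-up on baseline is ρk. The saving is never negative and is zero only at ρk = 1.

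**Equal SDs (k = 1).** The variance ratio is (1 + ρ)/2, so the saving is (1 − ρ)/2.

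| ρ | Variance ratio | Variance saved | SE saved, 1 − √ratio | ANCOVA N matching 450 by t-test | ANCOVA power where t-test has 80% |
|---|---|---|---|---|---|
| 0.3 | 0.65 | 35% | 19.4% | 292.5 | 93.5% |
| 0.5 | 0.75 | 25% | 13.4% | 337.5 | 89.9% |
| 0.7 | 0.85 | 15% | 7.8% | 382.5 | 86.0% |

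Matching N is 450 × ratio. Power is Φ((1.960 + 0.842)/√ratio − 1.960).

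**Other SD ratios: variance saved.**

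| k | ρ = 0.3 | ρ = 0.5 | ρ = 0.7 |
|---|---|---|---|
| 0.75 | 54% | 48% | 44% |
| 1.25 | 22% | 11% | 2% |
| 1.5 | 13% | 4% | 0.2% |

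Example, k = 0.75 and ρ = 0.3: (1 − 0.225)² / (1 + 0.5625 − 0.45) = 0.6006 / 1.1125 = 54%.

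**Effect of the floor.** The SAP rules were simulated with illustrative values: 450 subjects before the baseline exclusion, SD 1.5 log before flooring, baseline mean 3 log above the detection limit, no treatment effect, 1,500 trials per setting.

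| Follow-up mean | Share at floor | Observed k | Variance saved, ρ = 0.3 / 0.5 / 0.7 |
|---|---|---|---|
| Same as baseline | about 2% | 1.02–1.04 | 34% / 25% / 16% |
| 1 log lower | about 8% | 0.97–0.98 | 36% / 27% / 19% |
| 0.2 log above the limit | about 44% | 0.67 | 61% / 59% / 53% |

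In the last row the observed correlations are 0.255, 0.435 and 0.621. With k of about 0.67 they give slopes of roughly 0.17, 0.29 and 0.42, far from 1.

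**The case against.** **Baseline is not ignored, and the test is not biased.** This stands. The change score uses baseline with a fixed slope, and under randomization its expectation is the true effect. A reader might infer that chance baseline imbalance biases the result. Given an observed imbalance D, the change-score estimate is displaced by (ρk − 1)D, but this averages to zero over randomizations. It is part of the lost efficiency, not a separate bias.

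**A flat 15–35% loss cannot be stated as fact.** This stands. A reader might infer that range as a property of the plan. It needs equal SDs and ρ between 0.3 and 0.7, and the documents give neither. It is also a share of variance; the standard error moves only 8–19%. If titers spread out after baseline (k of 1.25 to 1.5), the gain can vanish.

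**The Day 7 gain depends on an unresolved rule.** This stands in part. Day 7 quantitative PCR is run only on RT-PCR-positive samples, and SAP 11.5.4 does not say whether an untested RT-PCR-negative sample counts as undetectable or missing. The 53–61% simulation row applies only if it counts as undetectable. If it counts as missing, few values sit at the floor and the Day 7 set is smaller and selected, which ANCOVA does not cure.

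**Omitting the strata is not an inconsistency.** This stands. The SAP stratifies its time-to-event tests, but its Fisher tests in 11.4.2 and 11.5.5 are also unstratified.

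**The analysis is exploratory.** This stands and limits the importance of the point. It does not remove the case for a change that costs so little.

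**Conclusion.** The point holds as one of efficiency. The planned t-test is valid, but less precise than ANCOVA on baseline log titer unless the slope of follow-up on baseline is exactly 1, and the detection-limit floor works against that. The covariate exists for every analysed subject, so adjustment drops nobody.

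The direction is certain in large samples; the size is not known. With equal SDs and a correlation of 0.3 to 0.7, both assumed, ANCOVA lowers the variance by 35% to 15%. Across the other SD ratios examined, the saving runs from about 0% to over 50%, and it may differ between days.

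It concerns three exploratory comparisons. A reader might infer a threat to the trial's main conclusions, but the documents do not support that: change in titer is outside the testing hierarchy in SAP 11.4, no power is claimed for it, and the type I error of the primary and secondary analyses is untouched.

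**What to change.** In SAP 11.5.4, replace the t-test at each of Days 2, 3 and 7 by ANCOVA with log titer as the outcome, and treatment, baseline log titer and the randomization factors (time from onset, pre-enrollment symptom relief medication, underlying lung condition) as covariates. Report the adjusted difference with its 95% confidence interval. Change the matching sentence in Protocol 8.4.1 too, so that the two documents do not diverge.

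The same edit of 11.5.4 can:

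- state whether an RT-PCR-negative Day 7 sample counts as undetectable or missing;
- correct the Derived Variables line, which defines time to return to usual health instead of change in titer.

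The cost is a few lines of text and minor programming, with no new data, visits or subjects. The change should be made before database lock. After lock, SAP section 7 would have it noted in the clinical study report as a deviation from the SAP.

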**Table 13: Variables Used for Analysis of Proportions of Subjects with Detectable Virus at Day 2, Day 3, or Day 7**

Variable	Source	Format/Notes
ePlex RPP RT-PCR or quantitative PCR result for Enterovirus/Rhinovirus	Laboratory Data	

Analysis

The proportion of subjects with a positive result for EV/RV by ePlex RPP RT-PCR or quantitative PCR at each of Days 2, 3, and 7 will be compared across treatment groups using a Fisher's exact test.

Analysis Population(s): ITTI

Derived Variables: Proportion of subjects with detectable virus at Day 2, 3, or 7 = number of subjects with "positive" result for EV/RV by ePlex RPP RT-PCR or quantitative PCR on Day 2, 3, or 7 divided by the total number of EV/RV-infected (ITTI) subjects with at least one test result for the time point for each treatment group.

NOTE: Day 2 and 3 visits were optional according to the protocol so it is expected that the number of subjects with test results at these time points will be less than the number of ITTI subjects.

**11.5.6. Time to Symptom Response for All Subjects Treated (ITT Population)**

Time to Symptom Response will be summarized for all subjects who received at least one dose of study medication regardless of viral infection (ITT population). A population-specific Symptom Response definition will be derived in accordance with [Section 11.2.1](#) for (1) the ITT population with underlying lung conditions and (2) for the ITT population without underlying lung conditions. Time to Symptom Response will be analyzed in accordance with [Section 11.2.2](#).

**11.5.7. Time to Ability to Perform All Normal Activities for All Subjects Treated (ITT Population)**

Time to Ability to Perform All Normal Activities as described in [Section 11.4.1](#) will be repeated for all subjects who received at least one dose of study medication regardless of viral infection (ITT population).

**11.5.8. Analysis of Proportions Experiencing Complications, All Subjects Treated (ITT Population)**

Analysis of Proportions Experiencing Complications as described in [Section 11.4.2](#) will be repeated for all subjects who received at least one dose of study medication regardless of viral infection (ITT population).

**11.5.9. Time to Symptom Response for Subjects Infected with Individual non-EV/RV Viruses or No Pathogen Detected**

Time to Symptom Response will be summarized for subgroups of subjects infected with the viruses shown below or with no pathogen detected provided that the subgroup includes at least 100 subjects.

Possible Subgroups:                    Influenza-infected  
    Parainfluenza-infected  
    hMPV-infected  
    Adenovirus-infected

Coronavirus-infected  
Bocavirus-infected  
No pathogen detected

A subgroup-specific Symptom Response definition will be derived in accordance with [Section 11.2.1](#) for (1) the specific virus-infected population with underlying lung conditions and (2) for the specific virus-infected population without underlying lung conditions. Time to Symptom Response will be analyzed in accordance with [Section 11.2.2](#).

#### **11.5.10. Analysis of Time to Symptom Response for Subjects Dosed Within 24 Hours of Symptom Onset**

Repeat the primary efficacy analysis for the ITTI population including only subjects who took the first dose of study medication within 24 hours ( $\leq 24$  hours) from symptom onset. Time from onset of illness will not be used as a factor in this analysis since all subjects will be from the same onset category.

Analysis Population(s): ITTI subjects with time of first dose of study medication  $\leq 24$  hours from symptom onset

Derived Variables: See [Section 11.2: Primary Efficacy Analysis](#)

#### **11.5.11. Analysis of Time to Symptom Response for Subjects Dosed $>24-\leq 36$ Hours after Symptom Onset**

Repeat the primary efficacy analysis for the ITTI population including only subjects who took the first dose of study medication more than 24 hours and less than or equal to 36 hours ( $> 24-\leq 36$  hours) from symptom onset. Time from onset of illness will not be used as a factor in this analysis since all subjects will be from the same onset category.

Analysis Population(s): ITTI subjects with time of first dose of study medication  $> 24$  and  $\leq 36$  hours from symptom onset

Derived Variables: See [Section 11.2: Primary Efficacy Analysis](#)

#### **11.5.12. Analysis of Time to Symptom Response for Subjects Dosed $>36$ Hours after Symptom Onset**

Repeat the primary efficacy analysis for the ITTI population including only subjects who took the first dose of study medication more than 36 hours ( $>36$  hours) from symptom onset. Time from onset of illness will not be used as a factor in this analysis since all subjects will be from the same onset category.

Analysis Population(s): ITTI subjects with time of first dose of study medication  $> 36$  hours from symptom onset

Derived Variables: See [Section 11.2: Primary Efficacy Analysis](#)

## 11.6. Other Exploratory Analyses

### 11.6.1. Population Pharmacokinetics Analysis

#### Variables Used for the Analysis

The analysis will require the following variables:

**Table 14: Variables Used for Analysis of Plasma Concentrations**

Variable	Source	Format/Notes
Day 3 tizoxanide (T) and tizoxanide glucuronide (TG) values	Laboratory data	
Demographic data	CRF	
Concomitant medications use	CRF	
Adverse events	CRF	

#### Analysis

Plasma concentrations of T and TG will be summarized descriptively for both treatment groups. Exploratory analyses will be conducted to evaluate relationships between plasma concentrations and age, race, gender, body weight, body mass index, concomitant medications (yes/no), changes in viral titer over time, Time to Symptom Response, and adverse events (yes/no). For continuous factors, the relationship with plasma concentrations will be assessed by Spearman's correlation analysis and Pearson's correlation analysis. For categorical factors, plasma concentrations will be compared among groups using the Kruskal-Wallis test.

Analysis Population(s): ITTI, NTZ-treated only

Derived Variables: Concomitant medication use: if any concomitant medication is used, then "yes", otherwise "no"

Adverse events: if any adverse event is reported, then "yes", otherwise "no"

Changes in viral titer over time: see [Section 11.5.5](#)

Time to Symptom Response: see [Section 11.2](#)

